#### 3.5.1. MODEL PERFORMANCE

The performance of a prediction model is typically assessed by its calibration and discrimination.

Calibration, which reflects how close the predictions from the model are to the observed outcome frequencies will be assessed graphically, using a calibration plot, plotting observed outcomes against predictions using smoothing techniques. The calibration plot will be supplemented with a smoothed regression line. Calibration will also be quantified by calculating the calibration slope and intercept.

The discrimination of the prediction models is the ability of the model to correctly rank individuals (i.e., those with the event should have higher predicted probabilities than those without), will be summarised with the concordance index (equivalent to the Area Under Receiver Operating Characteristic curve) with 95% confidence interval.

#### 3.6. SUB ANALYSIS

An additional analysis will be investigated to include patients with prior AF. Models (both regression model and machine learning approaches) will be developed to population include prior AF patient (compared to population for patients exclude prior AF). Model coefficients and performance will be compared between patients with and without prior AF.

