#### 3.1.2. EXCLUSION CRITERIA

- Patients who have requested that their data not be used for research
- Patients with paced rhythm
- The procedure was solely:
  - A transcatheter insertion of a valve or stent
  - An Isolated vascular procedure (aorta, pulmonary artery)
  - o A heart transplant
  - A lung transplant
  - For congenital heart disease

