#### 3.2. OUTCOME MEASURE

A new onset atrial fibrillation was defined as present if current atrial fibrillation or flutter was mentioned in patient cardiac report (e.g., ECG, ECHO) OR atrial fibrillation was identified by a trained chart abstractor for The Society of Thoracic Surgeons Adult Cardiac Surgery Database during postoperative period during the hospital admission (the outcome was assumed to happen within 7 days when timing was not specified).

Prior AF status was defined as any previous history of AF. Models for prior AF patients will be investigated in the sub analysis (section 3.6)

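### The prior-AF sub-analysis (SAP 3.6) has no baseline-rhythm rule, so AF already present at surgery is scored as a post-operative event and the planned comparison partly measures continuing AF

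*SAP*

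**What the plan says.** SAP 3.6 plans a secondary analysis: "An additional analysis will be investigated to include patients with prior AF". Regression and machine learning models are both refitted, and "Model coefficients and performance will be compared between patients with and without prior AF". No separate outcome is given, so the definition in SAP 3.2 carries over.

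That definition has two limbs. In the first, the event is "defined as present if current atrial fibrillation or flutter was mentioned in patient cardiac report (e.g., ECG, ECHO". In the second, "atrial fibrillation was identified by a trained chart abstractor for The Society of Thoracic Surgeons Adult Cardiac Surgery Database during postoperative period". A timing rule adds that "the outcome was assumed to happen within 7 days when timing was not specified".

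Prior AF is defined broadly: "Prior AF status was defined as any previous history of AF". Nothing separates past, resolved episodes from AF that is still present on the day of surgery. In the exclusion list of SAP 3.1.2 the only item about rhythm is "Patients with paced rhythm".

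The prediction target in SAP 2.1 is the risk that a patient develops AF within seven days of cardiac surgery. The protocol has no AF definition that would narrow the SAP 3.2 wording.

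**The concern.** A history of AF covers two kinds of patient. Some reach surgery in sinus rhythm and are at risk of a new episode. Others reach surgery already in AF. If the second kind stay in AF, the first post-operative ECG or chart review meets the SAP 3.2 criterion, although nothing has started after surgery.

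In the main models this hardly arises, because SAP 3.6 describes them as leaving out prior AF. The sub-analysis removes that protection and puts nothing in its place.

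At stake is the one comparison that SAP 3.6 exists to make. A larger prior-AF coefficient, or a different c-statistic in patients with prior AF, could reflect susceptibility to post-operative AF or simply the rhythm on arrival. The analysis as written cannot separate the two.

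**Working it through.** **Reading the sections together**

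1. Population: SAP 3.6 adds patients with any AF history (SAP 3.2).
2. Filter on baseline rhythm: paced rhythm only (SAP 3.1.2).
3. Event: current AF or flutter in a report, or AF found by the abstractor after surgery (SAP 3.2). Even if the post-operative period is read as applying to both limbs, AF that continues through surgery still qualifies.
4. Target: AF that develops after surgery (SAP 2.1).

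Steps 1 to 3 score continuing AF as an event; step 4 does not want it.

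**Inputs for the size**

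The plan gives no figure for SAP 3.6, so there is none to reproduce.

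- From the SAP: 20% event rate (3.3.2, 3.8.2) and a c-statistic of about 0.72 (3.8.2). A normal linear predictor with SD 0.87 at 20% prevalence gives a c-statistic of 0.72, so the anchor agrees with the SAP.
- Assumed: 15% or 25% of patients have prior AF; a share s of these, from 10% to 50%, is in AF at surgery; 90% of those are scored as events; the true odds ratio for prior AF in sinus rhythm is 2.

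**Share of prior-AF events that is continuing AF**

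The odds without prior AF are 0.20/0.80 = 0.25. Doubling the odds at each value of the linear predictor and averaging gives an event rate q of about 0.315 for prior-AF patients in sinus rhythm.

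Share = 0.9s / [0.9s + (1 − s)q]

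- s = 0.10: 0.090 / (0.090 + 0.2835) = 0.24
- s = 0.33: 0.297 / (0.297 + 0.2111) = 0.58
- s = 0.50: 0.450 / (0.450 + 0.1575) = 0.74

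**Crude odds ratio for prior AF**

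The denominators above are the event rates in the prior-AF group: 0.3735, 0.508 and 0.6075. Dividing their odds by 0.25 gives crude odds ratios of 2.4, 4.1 and 6.2. With no patient in AF at surgery the crude value is (0.315/0.685)/0.25 = 1.8. It lies below 2 because it is not adjusted for the linear predictor.

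**Fitted models**

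Logistic models in 500,000 simulated patients per scenario gave the following, with s from 10% to 50%.

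| Quantity | Patients in AF at surgery left out | Included, rhythm not a predictor | Included, rhythm a predictor |
|---|---|---|---|
| Prior-AF odds ratio | 2.0 | about 2.6-7.5 | about 2 |
| c-statistic within prior AF | about 0.72 | 0.60-0.68 | about 0.77-0.86 |

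For s of 33-50%, the whole-cohort c-statistic rises from 0.72-0.73 to 0.75-0.78, or to 0.77-0.82 with rhythm in the model.

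**Other coefficients**

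A separate simulation used prior-AF patients only, with post-operative AF rates near 20% or 40% in those not in AF at surgery. It had one ordinary risk marker (true coefficient about 0.82) and one marker linked only to being in AF at surgery (true coefficient 0). With 10%, 30% and 50% in AF at surgery, the ordinary coefficient fell to 0.59-0.69, 0.37-0.52 and 0.26-0.39. The rhythm-linked coefficient rose to 0.16-0.26, 0.35-0.47 and 0.42-0.53. Leaving out patients in AF at surgery restored about 0.82 and a c-statistic of about 0.71.

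**The case against.** SAP 3.2 names its outcome new-onset AF, and the aim is AF that develops after surgery. The SAP never says that continuing AF is to be counted. On this view the defect is an outcome left undefined for one subgroup, not a decision to score continuing AF. It is right that no such decision is documented. But the label has no criterion behind it for a patient with an AF history, and an analyst who applies the written criteria would score these patients as events.

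A reader might infer that the sub-analysis will make the model look better in patients with prior AF. The documents do not support this. The c-statistic within prior AF rises only if pre-operative rhythm is a predictor; otherwise it falls. Protocol 12.3 lists limited ECG findings as a likely data category but names no rhythm variable, and the Case Report Form that SAP 3.3.3 cites for the final predictors is not among the documents.

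A reader might also combine the inflated odds ratio with the high c-statistic. They do not occur in the same model: once rhythm is included, the odds ratio returns to about 2.

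Nor can it be said that the results would mostly reflect baseline rhythm. At 10% in AF at surgery, continuing AF is about a quarter of prior-AF events.

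Finally, this is one short secondary analysis. No primary outcome measure or sample-size figure depends on it. That stands and limits the weight of the point.

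**Conclusion.** The point holds for the sub-analysis. Followed as written, SAP 3.2 and 3.6 score AF already present at surgery as a post-operative event, and the comparison by prior-AF status partly measures continuing AF.

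The size rests on assumptions, because the documents give neither the share of patients with prior AF nor the share of those in AF at surgery. Over 10-50% in AF at surgery, with 90% of them scored as events and a true odds ratio of 2, continuing AF is about 24-74% of prior-AF events. Either the prior-AF odds ratio is inflated and the c-statistic within prior AF is too low, or the odds ratio is about right and that c-statistic is too high. Which one occurs depends on whether pre-operative rhythm is a predictor. Performance within prior AF is distorted either way.

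The main models, described as excluding prior AF, are largely unaffected.

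**What to change.** In SAP 3.6, before the sub-analysis is run:

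- Limit the prior-AF group used for fitting and performance to patients whose last pre-operative ECG shows neither AF nor flutter.
- Apply the same filter in any validation set in which the sub-analysis is run and pre-operative rhythm is recorded. SAP 3.6 does not itself say that the sub-analysis extends to the validation sets.
- Report patients in AF at surgery as a separate count, outside fitting and performance, and report how many have no recorded pre-operative rhythm.

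A separate, explicit outcome for prior-AF patients, or stratification by baseline rhythm, would also close the gap. The filter is the simplest because it leaves only patients at risk of a new episode on both sides of the comparison.

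The cost is a few lines of SAP text and one filter. ECG findings are already a data category in Protocol 12.3, but the documents do not establish that pre-operative rhythm is recorded in every dataset. The price is a smaller prior-AF group and the loss of patients with no recorded pre-operative rhythm.

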## 2. BACKGROUND

Atrial Fibrillation after cardiac surgery (AFACS) is the most common complication following cardiac surgery, with an incidence between 30% and 50%. The risk is higher for patients having either isolated mitral valve or combined mitral valve and coronary artery bypass graft surgery [1, 2]. Approximately 35,000 patients undergoing cardiac surgery in the UK every year. In the United States, approximately 500,000 patients undergo cardiac surgery annually [3]. AFACS is strongly associated with adverse patient outcomes, longer hospital and ICU stays, increased risk of stroke, increased risk of developing long-term AF (with associated complications and need for anticoagulation) and increased all-cause 30-day and 6-month mortality [4-9].

Even though AFACS can be transient, and patients are often discharged from hospital in normal sinus rhythm, patients with new-onset AFACS have a 5-fold increased risk of developing long-term AF [1]. A number of risk factors have been identified, including (older age, obesity) [10, 11], comorbidities (e.g., prior AF, hypertension, chronic kidney disease, obstructive sleep apnoea) [12], surgical features (e.g., valve surgery, increased aortic cross-clamp time, acute kidney injury) [13, 14] and the failure or inability to (re-)introduce Beta-Blockers. However, each of these factors only accounts for part of the overall risk [15]. Importantly, even when controlling for these confounding variables are, long-duration AFACS (> 2 days) is independently associated with decreased survival [16], as well as stroke and respiratory complications [17]. Current evidence therefore indicates that AFACS itself contributes to poor patient outcomes following cardiac surgery, and that tools to predict, prevent and guide treatment of AFACS are needed.

Currently, there is no widely accepted prediction model that reliably allows clinicians to determine the risk of a patient developing AFACS, despite multiple efforts over the past 15 years to develop one [18-21]. Published AFACS prediction models are limited by small sample sizes, a failure to include modern variables and a lack of external prospective validation [22-25]. Moreover, our team and others have previously developed AFACS risk prediction models that suffer from limited generalizability, oversimplification, and the fact that they often use information from variables that occur after surgery, or even after onset of AFACS [15, 24, 26].

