#### 3.3.2. SAMPLE SIZE CALCULATION

As the two models to be developed are predicting the same outcome (new onset AF in the 7 days after surgery), the same sample size is applicable to both models.

Data on approximately 12,000 surgeries are available from Massachusetts General Hospital between 2003 – 2020 with approximately 20% of patients having new onset AF in the 7 days after surgery.

We used formal sample size formulae for binary outcome measurement provided by Riley et al [28] and the associated 'pmsampsize'[29] sample size calculator in R statistical software programme to calculate the maximum number of candidate predictor parameters we can include during model development. Based on the prevalence and assuming an anticipated R squared between 5% and 15% of the max Cox-Snell R2 (i.e. Cox-Snell R2 between 0.0316 and 0.0948) we can examine up to 42 - 132 predictor parameters for inclusion in the model [28].

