#### 3.8.2. SAMPLE SIZE CALCULATION

Current recommendations for external validation sample size calculation uses 3 criteria (outlined below) [37]. We based the observed events/expected events (O/E) on the outcome prevalence (20%), the calibration slope (assuming model is well calibrated, intercept=0, slope=1), and on the c-statistic (15% of the max Nagelkerke's R-squared).[37-39]. We have assumed the linear predictor is normally distributed with a common variance in event and non-event groups, prior to model development. Given this strong assumption, we will update these calculations after model development is completed.

1. O/E calculation

We assume O/E is 1 in the external validation population, with a 95% confidence interval width of 0.2 for O/E. he estimated sample size to satisfy criterion 1 is 1538 patients (~308 events).

2. Calibration slope

We assume model is well calibrated with intercept=0 and slope=1. We also assume the linear predictor distribution is normally distributed. For a 95% confidence interval width of 0.2, we would need a sample size of 4248 patients (~850 events).

3. C-statistic

Based on 15% of R^2 (i.e., max 15% Cox-Snell R2 of ~0.09 based on assumed prevalence),

which equates to a C-statistic of ~0.72. Using this estimated C-statistic value with targeted a SE(C) of 0.025, correspond to a confidence interval of width 0.1 (i.e., 0.67-0.77), we would need a sample size of 619 patients (about 124 events). Varying the expected C-statistic from 0.67 to 0.77 and based on the assumption above, a sample size of 531 patients (106 events) to 691 patients (138 events) would be needed, respectively.

Therefore, a minimum sample size of 4248 patients with 850 (20% of 4248) events would be needed for external validation to satisfy all three criteria.

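### SAP 3.6 fits a mixed population against a subset of itself but promises a comparison of patients with and without prior AF; the stated fit would understate coefficient differences and can mislead on the c-statistic

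*SAP*

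**What the plan says.** SAP 3.2 defines the subgroup ("Prior AF status was defined as any previous history of AF") and announces that "Models for prior AF patients will be investigated in the sub analysis (section 3.6". That reads as a fit in prior-AF patients.

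SAP 3.6 then gives one fitting instruction, covering regression and machine learning alike. Models "will be developed to population include prior AF patient (compared to population for patients exclude prior AF"). The two populations are everyone, and everyone minus the prior-AF patients. The closing sentence states a different contrast: "Model coefficients and performance will be compared between patients with and without prior AF".

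The SAP does not say whether prior AF enters the mixed model as a predictor, whether prior-AF-by-predictor interactions are fitted, or whether performance is reported within each group. SAP 3.5.1 defines the c-statistic and the calibration slope and intercept without reference to strata. Neither document gives the number of prior-AF patients or their event rate.

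**The concern.** The two populations in the fitting instruction overlap almost completely, because one is the other with a minority added. Two consequences follow if that comparison is the one made.

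First, a coefficient from the mixed population is an average dominated by patients without prior AF. Its distance from the no-prior-AF coefficient is only a fraction of the distance between the two groups. Predictors that act quite differently in prior AF could be reported as acting alike.

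Second, the mixed-population c-statistic counts pairs made of one patient from each group. If prior AF is in the score and raises risk, those pairs are ordered well on balance, and C can go up although neither group is ranked any better. That could be reported as better performance once prior AF is included.

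Section 3.6 is where the SAP sends the reader for evidence in prior-AF patients, so the choice of comparison decides whether that evidence exists.

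**Working it through.** **Inputs from the SAP.** Event rate 20% (3.3.2: "approximately 20% of patients having new onset AF in the 7 days after surgery"; 3.3.4 says about 18%). Anticipated C of 0.72 (3.8.2: "which equates to a C-statistic of ~0.72"). Prior AF is named as a risk factor in the Background ("comorbidities (e.g., prior AF, hypertension, chronic kidney disease, obstructive sleep apnoea"), without a size.

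**Assumptions.** Prior-AF share 10-30%; prior-AF event rate 20-60%; the SAP's 20% taken as the rate without prior AF.

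**The SAP's own figure.** Section 3.6 states no number, so the anchor is the c-statistic sample size in 3.8.2. With φ = 0.20,

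SE² = C(1−C)·[1 + (n/2−1)(1−C)/(2−C) + (n/2−1)C/(1+C)] / [n²φ(1−φ)].

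At C = 0.72 and n = 619: 0.2016 × [1 + 308.5 × (0.2188 + 0.4186)] / (619² × 0.16) = 39.84 / 61,306 = 0.000650, so SE = 0.0255 = 0.1/3.92. The stated 619 is reproduced, as are 691 (C = 0.67) and 531 (C = 0.77). The figures follow the interval width of 0.1; an SE of exactly 0.025 would need 644.

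**Step 1: coefficients.** With prior AF as a main effect, the mixed slope is roughly an average of the group slopes, weighted by share × p(1−p). The fraction of the true difference that a mixed-against-excluded comparison shows is then about

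w = π·p₁(1−p₁) / [π·p₁(1−p₁) + (1−π)·p₀(1−p₀)],

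where π is the prior-AF share and p₁, p₀ are the event rates with and without prior AF. At π = 0.20, p₁ = 0.40, p₀ = 0.20: 0.048 / (0.048 + 0.128) = 0.27.

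A large-sample logistic simulation (1.5 million patients; true slopes 0.82 without and 0.41 with prior AF, difference −0.41) gave:

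| Prior-AF share | Difference shown | Fraction of truth |
|---|---|---|
| 10% | −0.05 to −0.06 | 12-16% |
| 20% | −0.09 to −0.12 | 22-29% |
| 30% | −0.13 to −0.17 | 32-41% |

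The ranges run over prior-AF event rates of 20%, 40% and 60%. Dilution is present even at equal event rates; it comes from the nesting.

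**Step 2: c-statistic.** Take a calibrated score, normal in events and non-events, with C = 0.72 in both groups. Its SD is s = √2·Φ⁻¹(0.72) = 0.824. For an event in group j and a non-event in group k, concordance is Φ[(logit pⱼ − logit pₖ + s²)/(s√2)]. At share 20% and rates 40% and 20%, the logits differ by 0.981:

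- within-group pairs: weight 0.08×0.12 + 0.16×0.64 = 0.1120, concordance 0.72
- prior-AF event against no-prior-AF non-event: weight 0.08×0.64 = 0.0512, concordance Φ(1.424) = 0.923
- no-prior-AF event against prior-AF non-event: weight 0.16×0.12 = 0.0192, concordance Φ(−0.259) = 0.398

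Mixed C = (0.0806 + 0.0472 + 0.0076) / 0.1824 = 0.743.

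The same formula gives the mixed C when C = 0.72 in both groups and prior AF is in the score:

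| Share | 20% rate | 30% | 40% | 50% | 60% |
|---|---|---|---|---|---|
| 10% | 0.720 | 0.724 | 0.734 | 0.746 | 0.761 |
| 20% | 0.720 | 0.727 | 0.743 | 0.763 | 0.785 |
| 30% | 0.720 | 0.729 | 0.749 | 0.773 | 0.799 |

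**Step 3: when C does not rise.** It stays at 0.720 if the event rates are equal, or if the score holds neither prior AF nor a correlate. If C within prior AF is 0.60 and the prior-AF rate is 30%, mixed C is 0.715, 0.707 and 0.699 at shares of 10%, 20% and 30%.

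**Step 4: both effects together.** In the step 1 simulation at 20% share and a 40% rate, the mixed model had C = 0.718 overall, 0.710 without prior AF and 0.612 with it. The overall figure is above the no-prior-AF figure although the score ranks prior-AF patients much worse.

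**The case against.** The best defence is that the right contrast is already in the text. The closing sentence of 3.6 names it, and SAP 3.2 can be read as a prior-AF fit. Comparing performance between the groups implies computing it in each, and a model fitted to everyone can still be assessed by group. Interactions are not ruled out either: SAP 3.3.3 seeks combinations of risk factors as candidates, and SAP 3.3.6 notes that machine learning models can use them. The analysis is additional, and no primary outcome rests on it.

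Much of this stands, and it limits what can be claimed. A reader might infer three stronger things that the documents do not support:

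- That the SAP has settled on mixed against excluded. It has not; two of its three statements point the other way.
- That the c-statistic will rise. The rise is conditional, as step 3 shows. Cross-group pairs are not all ordered correctly by prior AF: in the worked example 0.0192/0.0704, or 27%, of the cross-group pair weight is a no-prior-AF event against a prior-AF non-event, which prior-AF status orders wrongly. Where C does rise, ranking across the whole mixed population has really improved; only ranking within groups has not.
- That the analysis cannot say anything about prior-AF patients. It can, if performance is broken down by group.

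What the defence does not remove is that the only sentence telling the analyst what to fit describes nested populations, and no prior-AF-only fit, prior-AF interaction or within-group reporting is specified.

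**Conclusion.** SAP 3.6 is internally inconsistent and should be reworded. Followed literally, its fitting instruction would show a minority of any true coefficient difference: about 12-41% over assumed prior-AF shares of 10-30%. The percentages come from a regression with a prior-AF main effect and no interactions; a model that captures interactions would behave differently.

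The c-statistic problem is a possibility with stated conditions. With prior AF in the score, equal ranking in both groups and prior-AF event rates of 40-60%, mixed C is 0.734 to 0.799 against 0.72. At 30% the rise is under 0.01, and at equal rates there is none. For scale, the precision target in 3.8.2 is "targeted a SE(C) of 0.025, correspond to a confidence interval of width 0.1", a half-width of 0.05. At 20% share the rise is 0.023 (40% rate) to 0.065 (60% rate), so it could look meaningful.

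The dilution result is firm in direction. Both sizes depend on a prior-AF share and event rate that the documents do not give. The matter is confined to a secondary analysis.

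**What to change.** Reword SAP 3.6 so that the contrast is patients with prior AF against patients without it:

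- Specify either a separate model fitted in prior-AF patients, or one all-patient model with a prior-AF term and prior-AF-by-predictor interactions. Compare coefficients between the two separate fits or through the interactions.
- Report the c-statistic, calibration intercept and calibration slope within each group, for regression and machine learning models.
- State that mixed-population C set against no-prior-AF C will not be interpreted as a difference in performance.
- State the number of prior-AF patients and their event rate when known.

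The cost is SAP wording and either a few model terms or one extra fit. Intervals in the smaller prior-AF group will be wider and should be shown. No new data are needed, and no sample size or main-model result changes.

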11.7 The Level of Statistical Significance

The level of statistical significance will be set at p<0.05.

11.8 Procedure for Accounting for Missing, Unused, and Spurious Data.

To avoid excluding patients when developing and validating our models, we will use multiple imputation to impute missing values, under a missing at random assumption. Identifying the true underlying missing data mechanism from the available is rarely possible. Assumptions need to be made on the plausible mechanism, and approaches needed to be used. Under a missing completely at random mechanism.

Clinical Research Protocol Template version 15.0 CON © Copyright: The University of Oxford and Oxford University Hospitals NHS Foundation Trust 2019 Page 21 of 34

CONFIDENTIAL

(MCAR), the missingness mechanism does not depend on unobserved (unseen) data. Carrying out a complete case analysis will produce unbiased estimates (but with a loss precision if full data are observed). Under the missing at random (MAR) assumption, the missingness after conditioning on the observed data does not depend on the unobserved (unseen) data. Under this approach, we can apply approaches such as multiple imputation, by fitting a joint model to the observed data and impute the missing data, taking account of the uncertainty in the estimated parameters of this joint model. We feel this, MAR, approach makes a less strong and more realistic assumption than the MCAR approach. The MAR imputation model will include all variables considered for the multivariable model building, the outcome and any auxiliary variables that will help explain the missingness. The assumption of a missing not at random (MNAR) approach whilst not implausible is considerably more complex to investigate – there is a dearth of research investigating MNAR in the context of prediction model research. We will nevertheless explore whether the MAR assumption holds by comparing the imputed values (after accounting for the observed values) and the missing values to identify if there are any systematic differences to suggest a MNAR assumption.

Data from the NHS Trusts provide a large "real-world" prospective validation, but is likely to contain more missingness (60).

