#### 3.3.4. DURING MODELLING

In the Massachusetts General Hospital dataset, we anticipate that around 18% of patients will experience AFACS which was used to inform the sample size calculation. We will model the binary outcome using logistic regression. Though the risk of overfitting is low, given the high number of candidate predictors, we will also use shrinkage methods and specifically the Least Angle Selection and Shrinkage Operator (LASSO) to penalise and identify which predictors will be included in the final models [30].

Continuous variables will be kept as continuous in the model to avoid a loss of predictive information. Non-linear relationships with AFACS will be investigated using fractional polynomials or restricted cubic splines.

Since the development cohort spans an extended period, there is a chance that the calibration of the model will vary according to time. Therefore, we may consider re-calibrating the final model using the most recent subset of data [31].

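### SAP 3.6: comparing LASSO coefficients between patients with and without prior AF cannot by itself show that predictors act differently in the two groups

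*SAP*

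**What the plan says.** SAP 3.2 defines prior AF as any history of AF and adds: "Models for prior AF patients will be investigated in the sub analysis". SAP 3.6 says that regression and machine learning models "will be developed to population include prior AF patient (compared to population for patients exclude prior AF", and then: "Model coefficients and performance will be compared between patients with and without prior AF".

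The two sentences of 3.6 fit different designs. The first suggests overlapping populations (everyone, against those without prior AF). The second, like 3.2, suggests two disjoint groups.

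SAP 3.3.4 is the only place that describes how the regression models are built. LASSO is used "to penalise and identify which predictors will be included in the final models". Section 3.6 gives no other procedure and no predictor set common to the two fits. It also names no interaction term, interval or criterion for calling two coefficients different. The bootstrap in SAP 3.5 corrects performance for optimism and is not applied to coefficients.

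**The concern.** Comparing coefficients between groups asks whether predictors act differently in patients with prior AF. A LASSO coefficient does not answer that cleanly. Which predictors survive depends on sampling noise around the penalty threshold. How far the survivors are pulled towards zero depends on the penalty, which cross-validation tends to set higher in a smaller sample. Two fits from the same truth but of different size will therefore differ in membership and, systematically, in coefficient size. The smaller prior-AF group will tend to show weaker effects and a different list of predictors whether or not anything is modified.

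At stake is the interpretation of the sub-analysis. A side-by-side table would invite the reading that some predictors matter in only one group, or matter less after prior AF, when the method alone can produce that pattern.

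**Working it through.** **Inputs from the documents.** "Data on approximately 12,000 surgeries are available from Massachusetts General Hospital", with "approximately 20% of patients having new onset AF in the 7 days after surgery" (SAP 3.3.2). Cox-Snell R² is 0.0316 to 0.0948 (3.3.2), and the c-statistic is about 0.72 (3.8.2). The SAP's capacity statement is "we can examine up to 42 - 132 predictor parameters for inclusion in the model".

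**Assumptions not in the documents.** Prior-AF share of 10%, 20% or 30%; about half the candidates real; pairwise correlation 0.1; penalty chosen by 5-fold cross-validation; target shrinkage factor S = 0.9.

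**Step 1: reproduce the SAP's range.**
- Maximum Cox-Snell R² at 20% prevalence = 1 − exp{2[0.2 ln 0.2 + 0.8 ln 0.8]} = 0.632. Five and 15 per cent of this are 0.0316 and 0.0949.
- Parameters supported: P = n(S − 1) ln(1 − R²/S).
- At R² = 0.0316: 12,000 × 0.1 × 0.0357 = 42.9, so 42, as stated.
- At R² = 0.0948: 12,000 × 0.1 × 0.1113 = 133.6, so 133 against the stated 132. This is close enough.

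**Step 2: apply the same formula to the prior-AF group.** For 1,200, 2,400 or 3,600 patients, P is 4, 8 or 12 at R² 0.0316, and 13, 26 or 40 at R² 0.0948. All are below 42, so the prior-AF fit is the unstable side of the comparison.

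**Step 3: simulate identical effects in both groups.** 12,000 patients, 42 candidates, c-statistic about 0.71 to 0.72, each population with its own LASSO.
- Disjoint groups, 60 runs per scenario: mean keep/drop disagreements were 13.2, 12.5 and 11.7 of 42 at shares of 10%, 20% and 30%, and never fewer than 5 in any run. With a 43% event rate in the prior-AF group (20% share), the mean was 12.1.
- Same runs with the sparser one-standard-error penalty: 6.2 to 10.9.
- Separate simulation, prior-AF group of 1,200 or 2,400, 30 runs each: 13 to 14 disagreements. Two to 5 coefficients differed by more than 0.1 log-odds (odds ratio exp(0.1) = 1.11). Prior-AF coefficients were about 0.76 to 0.85 of the other group's.
- Overlapping populations: 5.5 to 7.3 disagreements in 10 runs per scenario. With 20 real effects of 0.03 to 0.45 log-odds and 12 runs per scenario, 3.9 to 7.9.
- That last effect pattern with disjoint groups gave 14.4 to 19.8 in one set of 12 runs and 11 to 13 in another of 8. These sets are small, so the 12 to 14 from the larger runs is the figure relied on.

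**Step 4: check the alternative.** A joint likelihood-ratio test of all 42 prior-AF interactions in unpenalised models rejected in 4.8% to 7.0% of 500 runs per scenario, against a nominal 5%. The 7.0% came from the smallest prior-AF group (1,200).

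**The case against.** **Much is inferred.** SAP 3.6 does not state that LASSO is rerun in each population, or that coefficients are read one at a time. That is fair. Separate fitting is the natural reading of 3.6 with 3.3.4, but it is not stated text, and a purely descriptive table makes no formal false claim. The SAP does not label the comparison descriptive, however, and the unequal shrinkage would be in the table either way.

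**The flips are mostly small.** About 10 of the disagreements involve predictors with no true effect. In one check the median coefficient kept by only one fit was about 0.02 log-odds per SD (odds ratio 1.02), and only 0 to 1.6 such coefficients per study exceeded 0.1. So the keep/drop count alone overstates the problem. It does not remove it: across all coefficients 2 to 5 differed by more than 0.1, and the shrinkage difference runs in one direction.

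**Three stronger readings are not supported.**
- A reader might infer a near-certain false positive: 1 − 0.95^42 = 88% or 1 − 0.95^132 = 99.9%. Those figures need a separate test of each coefficient at 5% (and independent tests). Protocol 11.7 says only "The level of statistical significance will be set at p<0.05", and the SAP plans no coefficient tests.
- A reader might take 42 to 132 as the number of comparisons. It is a ceiling on candidate parameters; the actual list is in the case report form, which is not among the documents.
- A reader might infer that the sub-analysis decides whether prior-AF patients get their own model. Neither document says so. The same sentence of 3.6 also compares performance, which is the more usual basis for that judgement.

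**Conclusion.** The concern holds in limited form. As planned, the coefficient comparison cannot separate effect modification from selection noise and sample-size-dependent shrinkage. With identical true effects and 42 candidates, expect about 12 to 14 keep/drop disagreements for disjoint groups under the cross-validated minimum penalty, fewer (6 to 11) under the sparser penalty, and about 4 to 8 for overlapping populations. Expect visibly smaller coefficients in the prior-AF group as well. The sizes rest on the assumed prior-AF share, effect pattern, correlation and tuning rule. The direction does not depend on which reading of the populations is taken.

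The performance half of the sentence is unaffected, and machine learning models such as random forests have no comparable coefficients. This is a weakness in a sub-analysis and does not touch the main models. It is worth correcting before analysis.

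**What to change.** In SAP 3.6, state which populations are compared, then replace the coefficient comparison with two steps.

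(a) Apply the main (no-prior-AF) model to prior-AF patients and report its calibration intercept, calibration slope and c-statistic with 95% confidence intervals. SAP 3.5.1 already defines these measures. They show whether the main model transfers, though not which individual effects differ.

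(b) Base any statement about differing predictor effects on one pooled, unpenalised logistic model with a pre-specified predictor set and prior-AF-by-predictor interactions. Report one joint test and the individual interactions with intervals, labelled exploratory. Choose the set with the size of the prior-AF group in mind, given the limits in Step 2 of the working. The joint test is one summary alongside (a) and need not act as a gatekeeper.

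Add a sentence that differences in LASSO selection or in shrunken coefficient size will not be interpreted as effect modification.

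The cost is SAP wording and one or two extra regressions on data already held. Individual predictor differences can then be presented only as exploratory, and a predictor that matters only after prior AF will be missed if it is outside the pre-specified set.
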